6.0 SAFETY MONITORING AND ADVERSE EVENT REPORTING

6.1 Safety Monitoring

All adverse events will be followed by the PI and study personnel until the events are resolved, the subject is lost to follow-up, or the adverse event is otherwise explained. At the last scheduled visit, the investigator will instruct each subject to report any subsequent event(s) that the subject, or the subject's personal physician, believes might reasonably be related to participation in this study. The investigator will follow any death or adverse event occurring at any time after a subject has discontinued or terminated study participation that may reasonably be related to this study. An internal audit will take place each month of the trial to insure that everything is well documented.

As each of the first five subjects completes the cross-over (visit 3), we will submit to the IRB a report on how the drug was tolerated. We will report all side effects, adverse events and subject concerns. In the event that one of the first 5 subjects withdraws from the study for reasons related to the drug, we will report immediately to the IRB via modification.

6.2 Adverse Event Definitions and Reporting Requirements

6.2.1 Adverse Event

Safety information will be assessed initially by subject interview. The clinical research coordinator is responsible for collecting and recording all clinical data. As these results are collected, all adverse events will be identified and reported to the principle Investigators within seven (7) days. Adverse events will be reported as described below (section 6.2.3). The principal investigator (PI) is responsible for evaluating each AE and for determining whether the AE affects the risk/benefit ratio of the study and whether modifications to the protocol and consent form are required. All IRB-approved protocol or consent form revisions that indicate a change in risk for participants will be reported to the National Institute of Diabetes and Digestive and Kidney Diseases (NIDDK) in a timely manner.

Study participants will be provided a telephone number and instructed to contact the study clinician to report any AEs they may experience, except for life-threatening events, for which they will be instructed to seek immediate emergency care. Where feasible and medically appropriate, participants will be encouraged to seek evaluation where the study clinician is based, and to request that the clinician be paged or otherwise contacted upon their arrival. With appropriate permission of the participant, whenever possible records from all non-study medical providers related to AEs will be obtained and required data elements will be recorded on study case report forms. All participants reporting an AE will be followed clinically, until the AE resolves (returns to baseline) or stabilizes.

Study site staff will document on study case report forms all AEs reported by or observed in enrolled study participants regardless of severity and presumed relationship to study product.

All adverse events will be graded as follows:

Severity

- 0 = No adverse event or within normal limits
- 1 = Mild—did not require treatment
- 2 = Moderate—resolved with treatment
- 3 = Severe—required professional medical attention
- 4 = Life-threatening or disabling
- 5 = Death

Related to study procedures (there is a reasonable possibility that the experience may have been caused by the study procedures)

- 0 = Unrelated
- 1 = Unknown
- 2 = Related

Unexpected event (an AE with specificity or severity not consistent with the risk information in the protocol/application or an AE that has not been previously observed)

0 = No1 = Yes

Serious (any AE occurring at any dose that results in death; a life-threatening adverse drug experience; inpatient hospitalization or prolongation of existing hospitalization; a persistent or significant disability/incapacity; a congenital anomaly/birth defect; or any important medical event that, based on medical judgment, jeopardizes the subject and may require medical or surgical intervention to prevent one of the above outcomes)

0 = No1 = Yes

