2.3 Study Design

Overview of study design

This is a placebo-controlled, double-blind crossover trial. There are 2 phases 14 days each separated by a 3-week washout period

A brief screening visit will assess eligibility criteria, and will include informed consent. Qualified participants will be stratified by diabetes status and randomly assigned (1:1) to 14 days of placebo followed by 14 days weeks of oral L-glutamine, or 14 days of oral L-glutamine followed by 14 days of placebo, each separated by a 3-week wash-out period.

Qualified participants will participate in 3 study visits, plus a screening visit. Study outcomes will be assessed at each of these 3 visits.

Subjects will receive 0.4 g/kg/day of L-glutamine in three divided daily doses. This dose was chosen based on a review of studies in the literature evaluating biological activity of glutamine on immune function and modulation of muscle turnover. Placebo will consist of identical appearing maltodextrin powder.

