6.2.3 Adverse Event Reporting

Any AE that is unexpected, related to study participation, and serious (defined in 6.2.1) will be reported in writing to the IRB within 7 days of the PI's first knowledge of the event. Any AE that is unexpected, related to study participation, and suggests greater risk of harm than previously known or recognized will be reported in writing to the IRB within 7 days of the PI's first knowledge of the event.

The PI will review all expedited adverse event reports. In addition, any deviations from protocol will be reported to the IRB and copied to the Prevention Center.

A summary of all adverse events and any audit reports will be sent to the IRB. Any action resulting in a temporary or permanent suspension of this study (e.g., IRB actions, or actions by the investigators or co-investigators) will be reported to the appropriate NIDDK program official. In addition, the NIDDK will be given notice of any actions taken by the IRB or regulatory bodies regarding the research and any responses to those actions.

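### Section 6.2.1 gives staff up to 7 days to report any adverse event to the PI, with no shorter limit for serious events, so an unexpected, related, serious event may take 14 days from collection to reach the IRB.

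*Combined protocol and SAP*

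**What the plan says.** Section 6.2.1 makes the research coordinator responsible for gathering the clinical data and then sets the internal limit: "all adverse events will be identified and reported to the principle Investigators within seven (7) days". The severity scale below it runs from 0 (no event) to 5 (death), and the limit does not vary with grade. The same section gives the PI the next step: "The principal investigator (PI) is responsible for evaluating each AE".

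Seriousness is a yes/no item in 6.2.1 and is defined again, with the same content, in 6.2.2. Neither place says how fast a serious event must reach the PI. Section 6.2.2 mentions expedited reporting only to list hospitalizations that do not need it. Section 6.2.3 has the PI review expedited reports without saying when they must arrive.

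The IRB limit in 6.2.3 applies to a narrow class: "Any AE that is unexpected, related to study participation, and serious (defined in 6.2.1"), plus unexpected, related events that point to more risk than was known. These events "will be reported in writing to the IRB within 7 days of the PI's first knowledge of the event". For the rest, 6.2.3 says only this: "A summary of all adverse events and any audit reports will be sent to the IRB", with no date.

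On treatment length, section 2.3 says: "There are 2 phases 14 days each separated by a 3-week washout period".

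**The concern.** The two limits run one after the other. Because the IRB clock waits for the PI's knowledge, any time allowed to staff is added in full to the time before the IRB is told. The protocol separates serious from other events for IRB reporting, but not for the step that triggers it. A coordinator who passes on a hospitalization or a death on the seventh day has complied.

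What is at stake is safety oversight. Under 6.2.1 the PI judges whether an event changes the study's risk/benefit balance and whether the protocol or consent form must change. That judgement cannot begin before the PI hears. The protocol itself says that the mechanism of any glutamine toxicity is unknown (4.4) and that its effect in this population is unclear (3.4). Sample size, power and type I error are not involved.

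**Working it through.** **Inputs**

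| Item | Value | Source |
|---|---|---|
| Staff to PI, all events | 7 days, as results are collected | 6.2.1 |
| PI to IRB, unexpected and related events that are serious or suggest greater risk | 7 days from PI's first knowledge | 6.2.3 |
| Treatment period | 14 days | 2.3 |
| Scheduled contacts after dispensing | calls on Days 7 and 45; visits on Days 15 and 53 | 5.0, Table 1 |
| Dosing blocks | Days 0–14 and 39–52 | Table 1 |

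The plan states each 7-day limit but not their total, so there is no stated total to reproduce.

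**Step 1: longest compliant time from collection to IRB.** Staff-to-PI limit + PI-to-IRB limit = 7 + 7 = 14 days. As a share of a treatment period, 14/14 = 1.

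**Step 2: time from onset.** The clock starts at collection, so onset-to-IRB time = collection day + 14 − onset day. Two assumptions give a range for period 1:

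- Collected on the day of onset: 14 days, whatever the onset day.
- Collected at the next scheduled contact, assuming the Day 7 call picks up events. Onset Day 1, collected Day 7: 7 + 14 − 1 = 20 days. Onset Day 8, collected Day 15: 15 + 14 − 8 = 21 days. Onset Day 14, collected Day 15: 15 + 14 − 14 = 15 days.

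The range is 14 to 21 days. Anything above 14 comes from late detection, not from the reporting clock.

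**Step 3: how much dosing the staff-to-PI step can span.**

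- Day 7 call: 7 + 7 = Day 14, the end of the first dosing block. Day 45 call: 45 + 7 = Day 52, the end of the second. The step itself is at most 7/14 = 50% of a period.
- Visit 2: 15 + 7 = Day 22, inside the Day 16–37 washout and 38 − 22 = 16 days before period 2 starts. Visit 3 on Day 53 follows the last dosing day. For events found at visits, the lag spans no dosing.

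**Step 4: does another provision shorten the staff-to-PI step?**

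- *Telephone line to the study clinician (6.2.1).* No clinician-to-PI time is given, and the clinician is not said to be the PI.
- *Emergency care and paging of the clinician (6.2.1).* These concern the participant's care and set no time for informing the PI.
- *First five subjects (6.1).* The immediate report goes to the IRB, and only when one of them withdraws for drug-related reasons.
- *Expedited reports (6.2.2, 6.2.3).* No time is given for them to reach the PI.

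None of them sets a shorter limit.

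**The case against.** The strongest reply is that the 7-day sentence follows one about collecting and recording data. It can be read as an outer limit for routine data flow, with acute care handled elsewhere: participants may phone the clinician about any event, are sent to emergency care for life-threatening ones, and are encouraged to have the clinician paged. In practice staff would probably report a serious event much sooner. No document sets a next-working-day standard.

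Much of this stands as regards patient care, and it rules out three stronger readings that a reader might infer:

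- *Most of a dosing period passes before anyone can act.* The step is at most half a period, and for events found at visits it spans no dosing. Only the Day 7 and Day 45 calls fall within dosing, and section 5.0 describes them as adherence and reminder calls.
- *The toxicity actions in 4.4 wait for the PI.* Section 4.4 names no actor, 3.6 refers to the investigator, and 6.2.1 separately mentions a study clinician. Nothing makes those actions depend on notice to the PI.
- *Any adverse event may take 14 days to reach the IRB.* The second 7-day limit covers only the narrow class in 6.2.3. Other events go in a summary with no date.

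The reply does not remove the gap. The wording covers all adverse events without exception, and good practice by staff is no substitute for a stated limit on serious ones.

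**Conclusion.** The point holds for the reporting chain only. Serious events have no shorter staff-to-PI limit, and for an unexpected, related, serious event 14 days from collection to IRB report is compliant. That maximum assumes both limits are used in full and that the PI does not hear by another route. Counted from onset it is 14 to 21 days under the detection assumptions above. It is not evidence that such delays would be usual.

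The documents do not support a claim that participants would go on being dosed because of this rule, and none is made here. This is a cheap improvement to safety oversight with no bearing on the analysis.

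**What to change.** In 6.2.1, add a separate, shorter staff-to-PI limit for events meeting the 6.2.2 definition of serious, for example by the next working day after staff become aware. Keep 7 days for all other events. State that the clock starts at staff awareness. Since 6.2.3 points to the definition in 6.2.1, cite one definition throughout.

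Under the example, the longest compliant time from awareness to IRB falls from 14 days to 1 + 7 = 8 when the next day is a working day, or 3 + 7 = 10 from a Friday to a Monday; holidays would add to this.

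The trigger should be seriousness alone. Tying it to 4.4 would bring in nearly every possibly drug-related event, mild ones included, and would ask coordinators to judge relatedness before the PI has seen the event.

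The cost is a sentence of protocol text and a brief staff instruction for 20 participants, or up to 30 under 4.3. No change to dosing, withdrawal or other clinical actions is proposed.

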6.2.2 Serious Adverse Event

Serious adverse event (SAE) will be defined per U.S. Code of Federal Regulations (CFR) 312.32 and International Conference on Harmonization (ICH), "Good Clinical Practice: Consolidated Guidance" (E6) and "Clinical Safety Data Management: Definitions and Standards for Expedited Reporting" (E2A), as AE occurring at any dose that:

- Results in death
- Is life-threatening

- Results in persistent or significant disability/incapacity
- Is a congenital anomaly/birth defect
- Requires inpatient hospitalization or prolongation of existing hospitalization

This includes important medical events that may not be immediately life-threatening or result in death, or hospitalization but may jeopardize the patient or may require intervention to prevent one of the outcomes listed above.

Per ICH SAE definition, hospitalization itself is not an adverse event, but is an outcome of the event. The following types of hospitalization do not require expedited reporting:

- Any admission unrelated to an AE (e.g. for labor/delivery, cosmetic surgery, administrative, or social admission for temporary placement for lack of place to sleep)
- Protocol-specified admission (e.g. for procedure required by protocol)
- Admission for diagnosis or therapy of a condition that existed before receipt of study agent(s) and has not increased in severity or frequency as judged by the clinical investigator

6.2.3 Adverse Event Reporting

Any AE that is unexpected, related to study participation, and serious (defined in 6.2.1) will be reported in writing to the IRB within 7 days of the PI's first knowledge of the event. Any AE that is unexpected, related to study participation, and suggests greater risk of harm than previously known or recognized will be reported in writing to the IRB within 7 days of the PI's first knowledge of the event.

The PI will review all expedited adverse event reports. In addition, any deviations from protocol will be reported to the IRB and copied to the Prevention Center.

A summary of all adverse events and any audit reports will be sent to the IRB. Any action resulting in a temporary or permanent suspension of this study (e.g., IRB actions, or actions by the investigators or co-investigators) will be reported to the appropriate NIDDK program official. In addition, the NIDDK will be given notice of any actions taken by the IRB or regulatory bodies regarding the research and any responses to those actions.

7.0 STATISTICAL CONSIDERATIONS

7.1 Review of Study Design

We propose a single-center double blind randomized cross-over trial of glutamine supplementation versus placebo. As part of the study there will be a 4-week washout between treatment and placebo arms.

7.2 Endpoints

Primary endpoints are change in mitochondrial energetics and endothelial function. Secondary endpoints are change in metabolic response profile and markers of oxidative stress and inflammation.

7.2.1 Primary Endpoints

Consistent with the primary study objective to test for glutamine's impact on endothelial function and mitochondrial function, the following endpoints will be assessed:

- Improvement in mitochondrial function as measured by ³¹P MRS/OS parameters of ATP_{max} and Oxygen uptake (O_{2max}) and the ATP_{flux}/O_{2uptake} ratio representing the efficiency of mitochondria energy production.
- Improvement in vascular function as measured by the difference in the spectroscopic delay in recovery of oxygenated myoglobin and oxygenated hemoglobin after the onset of reperfusion during optical spectroscopy.

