2.0 STUDY OBJECTIVES AND DESIGN

2.1 Primary Objectives

The primary objectives of this study are to:

• To test if glutamine supplementation improves mitochondrial function and vascular function as measured by ³¹P MRS/OS.

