4.3 Adherence Assessment

Adherence to the study treatment will be assessed by study coordinator phone call at day 7 of the study to assess adherence and inventory method to assess remaining medication/placebo at the end of the study. Adherence will be defined as consumption of at least 75% of the prescribed regimen. Up to 30 participants may be recruited to compensate for non-adherence or drop-out with the goal of 10 individuals completing in each treatment arm.

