7.3 Accrual, Follow-up, and Sample Size

The overall sample size for this project is 20. We anticipate recruiting 1-2 participants weekly for total study duration of 2 years.

Sample size was calculated based on values obtained from an estimated within individual coefficient of variation in values of ATP/O₂ ratio from MRS/OS of approximately 15% and values of test-retest reliability of pulse amplitude tonometry measures of vascular endothelial function from a recent published study. A total of 20 patients will enter this two-treatment crossover study. With this sample size, the probability is over 90% that we will detect a meaningful treatment difference of 20% for ATP/O2 ratio at a one-sided 0.05 significance level (Table 2). This is based on the assumption that the within-patient standard deviation of the response variable is 0.375 with a mean predicted ATP/O2 ratio of 2.5. Sample size was calculated using the following sample size calculator: http://hedwig.mgh.harvard.edu/sample_size/js/js_crossover_quant.html

	ATP/O ₂ ratio	
	Power	
Minimal detectable difference	80%	90%
20%	6	7
25%	4	5
33%	4	4
40%	3	4

Table 2. Samples size required to detect treatment effects for ATP/O2 ratio from MRS/OS and reactive hyperemia index (RHI) from PAT in crossover design.

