7.6 Data Analysis

7.6.1 Primary Analyses

The major assumption in the cross-over trial is that there is no carryover effect of first period into the second period. The assumption is that a 3-week washout will be sufficient

to eliminate any potential carryover effect due to glutamine. The statistical model we assumed for continuous data from the 2×2 crossover trial:

Design	Period 1	Period 2
Sequence Placebo-Gln	A	В
Sequence Gln-Placebo	В	A

From this design we construct these differences for every patient and compare the two sequences with respect to these differences using a two-sample paired t test. Thus, we are testing:

$$H_0: \mu_{AB} - \mu_{BA} = 0$$

Where:
$$\mu_{AB} - \mu_{BA} = 2(\mu_A - \mu_B)$$

So testing
$$H_0: \mu_{AB} - \mu_{BA} = 0$$
, is equivalent to testing:

$$H_0: \mu_A - \mu_B = 0$$

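### Four unranked primary measures, and a primary analysis with no success rule, test level or multiplicity control

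*Combined protocol and SAP*

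**What the plan says.** All references are to the combined protocol and SAP.

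- **Objective (2.1).** "To test if glutamine supplementation improves mitochondrial function and vascular function as measured by" MRS/OS. Two domains are named together.
- **Primary endpoints (7.2.1).** The list is introduced with "impact on endothelial function and mitochondrial function, the following endpoints will be assessed". The mitochondrial item covers "parameters of ATP_{max} and Oxygen uptake (O_{2max}) and the ATP_{flux}/O_{2uptake} ratio", which is three measures. The vascular item is "Improvement in vascular function as measured by the difference in the spectroscopic delay in recovery of oxygenated myoglobin and oxygenated hemoglobin", a fourth. None is ranked above another.
- **Primary analysis (7.6.1).** Period differences are formed for each patient, and the plan is to "compare the two sequences with respect to these differences using a two-sample paired t test", against a null of no treatment difference. The section names no endpoint, level or sidedness. It does not say how many measures must succeed and describes no adjustment.
- **Sample size (7.3).** With 20 patients the plan claims over 90% power to "detect a meaningful treatment difference of 20% for ATP/O2 ratio at a one-sided 0.05 significance level". This is the only significance level in the document, and it is not carried into 7.6.1. No other 7.2.1 measure has an effect size, SD or power figure. For vascular function, 7.3 and the Table 2 caption refer to pulse amplitude tonometry and the reactive hyperemia index (RHI), not to the optical delay.

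**The concern.** Four measures hold primary status and each can be put through the same test. The plan does not say whether one success supports a claim of benefit, whether each domain needs one, or whether all four are required. Two analysts following the text could draw opposite conclusions from the same data, and the rule could be settled after the results are known. The false-claim rate is a property of that rule, so the plan as written does not fix it.

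**Working it through.** **Inputs.** Four measures, three mitochondrial and one vascular (7.2.1). One-sided 0.05 (7.3). N = 20, randomized 1:1 to two sequences (2.3, 7.3), with a target of 20 completers: "with the goal of 10 individuals completing in each treatment arm" (4.3). For ATP/O2: "within-patient standard deviation of the response variable is 0.375 with a mean predicted ATP/O2 ratio of 2.5", and a 20% difference, so δ = 0.20 × 2.5 = 0.5 (7.3). The documents give no correlation between measures; I assume a common value from 0 to 0.9.

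**Step 1: the plan's own figure.** Exact noncentral-t power, one-sided 0.05, N − 1 df, with 0.375 as the SD of the within-patient difference, gives 6/7, 4/5, 4/4 and 3/4 patients for 80%/90% power. That matches all eight cells of Table 2. If 0.375 is instead the within-patient SD, as the text says, the SD of the difference is 0.375 × √2 = 0.530 and the cells would be 9/12, 7/8, 5/6 and 4/5. I carry both readings. With N = 20, 18 df and one-sided 0.05, power is above 99.9% on the first and 99.2% on the second, so the claim of over 90% holds either way.

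**Step 2: false-claim rate by rule.** Each test is at one-sided 0.05 and no measure is truly affected. Under independence:

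- any one of four: 1 − 0.95⁴ = 18.5%
- any one of three mitochondrial: 1 − 0.95³ = 14.3%
- one mitochondrial and the delay: 0.05 × 14.3% = 0.7%
- all four: 0.05⁴, which rounds to 0.0%

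For correlated measures, trials were simulated with 18-df t statistics (600,000 per correlation):

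| Rule | 0 | 0.3 | 0.5 | 0.7 | 0.9 |
|---|---|---|---|---|---|
| Any one of four | 18.5% | 16.5% | 14.7% | 12.3% | 8.9% |
| Any one of three mitochondrial | 14.3% | 13.1% | 12.0% | 10.4% | 8.1% |

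Over the same range, the rule needing one mitochondrial measure and the delay rises from 0.7% to 4.1%, and the all-four rule from 0.0% to 2.1%. If O2max and the ratio are negatively correlated (−0.3 to −0.7) and the rest independent, any one of four gives 18.8%. No correlation can take it above 4 × 0.05 = 20%.

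**Step 3: when one domain truly responds.** Suppose the delay improves and is detected. The two-domain rule then reduces to needing any one of three mitochondrial tests, so a false mitochondrial claim passes at 14.3% to 8.1%. The all-four rule stays at or below 5% whenever at least one measure is unaffected.

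**Step 4: with Holm adjustment.** The steps are 0.0125, 0.0167, 0.025 and 0.05. With no measure affected, the familywise rate is 4.9% at correlation 0, falling to 2.6% at 0.9. ATP/O2 power at the strictest step (0.0125), with 20 completers and 18 df:

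| SD of the difference | One-sided | Two-sided |
|---|---|---|
| 0.530 | 95.3% | 91.0% |
| 0.375 | 99.9% | 99.8% |

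**The case against.** The best counter-argument is that the text leans away from an any-success rule. Section 2.1 joins mitochondrial and vascular function, 7.2 names two primary endpoints rather than four, and 7.2.1 groups the three mitochondrial measures in one item. Under a two-domain rule the rate with no true effect is below 5%. This stands as a limit on the headline figure. It does not supply the rule: the joining word describes what is studied, three measures within a domain still need a rule, and Step 3 shows that a two-domain rule alone does not protect the mitochondrial claim.

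Second, all four measures come from one MRS/OS procedure on one muscle, so zero correlation may be the least realistic case. At 0.7 to 0.9 the any-of-four rate is 12.3% to 8.9%. That tempers the size but leaves it above 5%.

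Third, ATP/O2 is the only 7.2.1 measure with a power calculation, so a reader might infer that it leads. No section says so. If that is the intention, one sentence would settle the matter.

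Fourth, this is a single-center phase II crossover in 20 patients. That limits the consequences, but the plan still sets formal hypotheses and a power target.

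**Conclusion.** The omission is real and should be fixed. Four primary measures are unranked, and 7.6.1 has no success rule, level or multiplicity control. With no true effect and each test at one-sided 0.05, the false-claim rate runs from near 0% to 18.5% over correlations of 0 to 0.9, depending on the rule chosen.

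A reader might infer that the trial has an 18.5% false-positive rate. The documents do not support that. The figure needs an any-success rule that the plan does not state, 0.05 carried over from 7.3 to every test, and zero correlation. Nor should one conclude that the document contains no significance level, or that ATP/O2 is underpowered: 7.3 gives a level for that measure, and its power claim reproduces. The correlations are my assumption. The finding that no rule is stated rests on the text alone.

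**What to change.** Before unblinding, amend 7.6.1 in one of two ways.

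**(a) Single primary.** Name the ATP/O2 ratio as the only primary measure, tested at the 7.3 level, and make ATPmax, O2max and the optical delay secondary. ATP/O2 power is unchanged, above 99% with 20 completers on either reading of the SD. The cost is that the other three no longer support a primary claim. Vascular function would then leave the primary objective, so 2.1, 7.2 and 7.2.1 must be aligned.

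**(b) Four primaries with Holm.** Possible wording: *ATPmax, O2max, the ATP/O2 ratio and the optical delay are tested with Holm adjustment at familywise one-sided 0.05, in the direction of improvement stated for each. Mitochondrial benefit is claimed only if a mitochondrial measure is Holm-significant, and vascular benefit only if the optical delay is.* On the less favourable SD reading, ATP/O2 power with 20 completers falls from 99.2% to no lower than 95.3% (91.0% if two-sided). With 18 completers the floor is 92.4% (86.5% if two-sided). The loss for the other three measures cannot be computed from the documents. If two-sided tests are preferred, change 7.3 and 7.6.1 together.

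The choice between (a) and (b) is the sponsor's. Under either, 7.3 should restate ATP/O2 power at the chosen level and reconcile the vascular measure named there (pulse amplitude tonometry/RHI) with the optical delay in 7.2.1. An RHI column may have been lost from Table 2 when the text was extracted, so check the source file before concluding that no vascular sample size was given. The change is wording only, with no new participants or procedures.
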